3.3 Dose Justification

The IP formulation strengths (1.0% and 0.5%) proposed for the study were selected based on their previous use in a phase 1 study in healthy adult human subjects and are further supported by extensive non-clinical and pre-clinical testing in animal models.

See the Investigator's Brochure for additional information.

CONFIDENTIAL

3.4 End of Study Definition

A subject is considered to have completed the study if the subject has completed the last visit or the last scheduled procedure shown in the Schedule of Procedures and Assessments ([Appendix 1: Schedule of Procedures and Assessment](#)). The end of the study is defined as completion of the last visit or procedure shown in the schedule in the study globally.

CONFIDENTIAL

4 Study Population

The study population will consist of subjects who have undergone routine unilateral CELR surgery via phacoemulsification without surgical complication.

4.1 Inclusion Criteria

Subjects who meet all inclusion criteria at Visit 1 (Screening) and/or Visit 3 (Baseline/Randomization) will be eligible for study participation.

1. ≥ 21 years of age and in good general health at Visit 1 (Screening)
2. Willing and able to provide informed consent and provide relevant privacy authorization(s)
3. Willing and able to comply with study requirements and visit schedule
4. Clear ocular media (other than cataract) in the study eye
5. Planning to undergo routine unilateral CELR surgery via phacoemulsification extraction and implantation of an intraocular lens. **Allowed** in the study eye at Visit 2 (Day of Surgery):
 - a. Limbal relaxing incisions (laser-assisted and non-laser)
 - b. Intracameral injections and intracameral medications, excluding those identified in Exclusion Criterion #2
6. At Visit 1 (Screening), has the potential, in the opinion of the Investigator, for postoperative best corrected visual acuity (BCVA) ≤ 0.2 Logarithm of the Minimum Angle of Resolution (LogMAR) (i.e., 20/32 Snellen or better) in the study eye as assessed using Early Treatment Diabetic Retinopathy Study (ETDRS)
7. At Visit 1 (Screening), has BCVA ≤ 1.0 LogMAR (i.e., 20/200 Snellen) in the non-study eye due to pathology other than cataract as assessed using ETDRS
8. Able to self-administer eye drops
9. At Visit 3 (Baseline/Randomization; Day 1), has ACC Grade ≥ 2 in the study eye

4.2 Exclusion Criteria

Subjects who meet any of the following exclusion criteria will not be eligible for study participation.

Ophthalmic (Either Eye)

1. Any ocular pain at Visit 1 (Screening)
2. Used within 1 week before Visit 2 (Day of Surgery), or be planning to use during the study, corticosteroids, oral or topical non-steroidal anti-inflammatory drugs (NSAIDs), or Omidria® (i.e., phenylephrine and ketorolac injection).

Note: Low-dose acetylsalicylic acid (i.e., baby aspirin or similar) is allowed

CONFIDENTIAL

3. Moderate to severe lid, conjunctival, or corneal findings at Visit 1 (Screening)
4. Corneal abnormality (e.g., stromal, epithelial, or endothelial dystrophies, including epithelial basement membrane dystrophy)
5. History of chronic/recurrent inflammatory eye disease (e.g., scleritis, any uveitis, herpes keratitis)
6. Any signs of intraocular inflammation (cell/flare) at Visit 1 (Screening)
7. IOP ≥ 24 mmHg at Visit 1 (Screening)

Ophthalmic (Study Eye)

8. Using or unwilling to forgo contact lens use within defined windows before Visit 2 (Day of Surgery) and for the duration of the study
 - a. Polymethyl methacrylate contact lenses (6 months before surgery and throughout study)
 - b. Gas permeable rigid lenses (1 month before surgery and throughout study)
 - c. Extended wear or daily soft lenses (7 days before surgery and throughout study)
9. Known pathology that may affect visual acuity, particularly retinal changes that affect vision (e.g., macular degeneration, cystoid macular edema, proliferative diabetic retinopathy)
10. Capsule or zonular abnormalities with pre-operative crystalline lens tilt or decentration (e.g., Marfan's syndrome) or abnormalities that may affect post-operative centration or tilt of the crystalline lens (e.g., pseudoexfoliation syndrome)
11. History of moderate to severe ocular trauma with the possibility of previous zonule dehiscence
12. Ocular or periocular surgical interventions within defined windows before Visit 1 (Screening)
 - a. Microinvasive glaucoma surgery, any incisional ocular surgery, or intracameral drug depot to lower IOP (any history)
 - b. Intraocular surgery (6 months)
 - c. Laser surgery, limbal relaxing incision procedure, eyelid surgery (3 months)
13. Pupil abnormalities (e.g., non-reactive, tonic pupils, abnormally shaped pupils, pupils that do not dilate at least 3.5 mm under mesopic/scotopic conditions)
14. Keratoconus or significant irregular astigmatism on pre-operative ocular topography
15. Have a condition, or be in a situation, that may put the subject at significant risk of complex surgery and surgical complications that would lead to withdrawal from the study

Ophthalmic (Non-study Eye)

16. Underwent cataract surgery < 14 days before Visit 1 (Screening) or, during the study, will require cataract surgery < 1 day after Visit 2 (Day of Surgery)

CONFIDENTIAL

General

17. Within 30 days before Visit 1 (Screening), participated in an investigational drug or device study, or have used an investigational drug or device
18. Allergy or hypersensitivity to the IP or its excipients
19. Significant systemic disease (e.g., uncontrolled diabetes; myasthenia gravis; hepatic, renal, cardiovascular, or endocrine disorders)
20. Uncontrolled systemic disease, defined as, within 30 days before Visit 1 (Screening), a change in disease status or medications that may put the subject at increased risk or confound interpretation of study results
21. Changes within 30 days before Visit 1 (Screening), or anticipated changes during the study, to the dosage of systemic medication that could have a substantial effect on IOP
22. Known bleeding tendencies
23. Acute or chronic disease or illness that would put the subject at increased risk or confound interpretation of study results (e.g., autoimmune disease, connective tissue disease, immunodeficiency, suspected glaucoma, glaucomatous changes in the fundus or visual field, ocular inflammation, etc.)
24. Requires, is likely to require, or is unwilling to discontinue the use of prohibited medications
25. Pregnant, nursing, or planning a pregnancy during the study
26. Unwilling or unable to use an acceptable method of contraception throughout the study if a woman of childbearing potential (WOCBP; [Appendix 2: Woman of Childbearing Potential \(WOCBP\)](#))
27. Unwilling or unable to use an acceptable method of contraception throughout the study if a male sexual partner of a WOCBP

4.3 Screen Failures

Screen failures are defined as subjects who consent to participate in the study but who are not subsequently randomly assigned to IP and entered in the study. A minimal set of screen failure information is required to ensure transparent reporting of screen failure subjects, to meet the Consolidated Standards of Reporting Trials publishing requirements, and to respond to queries from regulatory authorities. Minimal information includes demography, screen failure details, eligibility criteria, and any serious adverse event (SAE), or non-serious AEs.

Prospective subjects who do not meet the criteria for study participation (screen failure) because of transient conditions that are expected to change, including but not limited to screen failures for high IOP, may be rescreened at Investigator discretion (maximum of 1 rescreen per prospective subject). Rescreened subjects should be assigned a new subject identification number, and the original subject identification number should be recorded as a screen failure.

CONFIDENTIAL

5 Study Treatment(s) or Intervention(s)

5.1 Investigational Products

Three (3) IPs will be administered during the study:

- VVN461, 1.0%
- VVN461, 0.5%
- Vehicle

The matching Vehicle will be identical to the active doses of IP, except Vehicle will not contain the active pharmaceutical ingredient (API). All IP will be administered topically to the study eye as eye drops.

5.1.1 Description

Both formulations of VVN461 and the matching Vehicle are colorless to light yellow sterile solutions packaged in 5 mL multidose low-density polyethylene eye drop bottles. The IP will be provided in identical primary packaging. IP will be supplied to sites in cartons. Each carton will contain 1 low-density polyethylene eye drop bottle.

5.1.2 Dosage and Administration

Subjects will be randomized to 1 of 3 possible groups in a 1:1:1 ratio. Study personnel will provide training to subjects on proper eye drop administration, proper IP storage when not in use, and proper use of the dosing diary.

All subjects, irrespective of group, will administer 1 eye drop in the study eye QID for a period of 14 days. If the subject misses their eye while administering an eye drop, a second eye drop may be administered. If the subject misses their eye while administering a second eye drop, a third eye drop may not be administered. The missed dose should be recorded in the dosing diary.

If a subject forgets or misses a scheduled dose of IP, the subject should administer the missed dose as soon as possible. The missed dose should be recorded in the dosing diary. The QID dosing schedule should then be resumed. Subjects will administer their first dose of IP and make their first dosing diary entry in the clinic under the supervision of study personnel to ensure proper dosing technique and dosing diary use.

CONFIDENTIAL

5.2 Preparation/Storage/Handling/Accountability

5.2.1 Acquisition and Accountability

IP will be provided to each site. Once the IP has been delivered to the site, it will be stored in a limited-access area only accessible to trained study personnel. Used and unused IP will be maintained at the site for accountability by the clinical study monitor.

When authorized by the Sponsor, and after the clinical study monitor has verified drug accountability is complete and accurate, used and unused IP either will be returned to the Sponsor or designee, or will be disposed/destroyed by the sites in accordance with the requirements of applicable local authorities and regulatory bodies to ensure disposal of IP does not expose human beings to risks from the drug.

5.2.2 Product Formulation, Appearance, Packaging, and Labeling

IP will be delivered to sites in identical packaging and labeled in accordance with federal regulations for investigational new drugs. Labels will include verbatim the following statement: "Caution: New Drug – Limited by Federal law to investigational use."

The formulation includes polyethylene glycol (a cosolvent), hydroxypropyl beta-cyclodextrin (a solubilizer), citric acid (a pH buffer), sodium citrate (a pH buffer), sodium chloride (a tonicity agent), and a preservative, benzalkonium chloride 0.02% (w/v). Water for injection is used as the final diluent for this product. There are no novel excipients used in the formulation. The product is manufactured aseptically and is intended to be used as a sterile product as Vehicle (0.0% VVN461), 0.5% VVN461, and 1.0% VVN461.

Additional details may also be included on the label, provided that these details do not pose a risk to study masking. This may include but is not limited to the protocol number, IP volume per container, storage requirements, manufacturer, and lot number.

5.2.3 Product Storage and Stability

IP will be stored at ambient room temperature (15°C to 25°C [59°F to 77°F]) and protected from light in a limited-access area accessible only to trained study personnel. One-day temperature excursions during handling, warehousing, and shipping operations are permitted up to 40°C (104°F), based on stability data.

Opened and unopened bottles of IP will be maintained at the site for accountability by the clinical study monitor.

CONFIDENTIAL

5.3 Measures to Minimize Bias: Randomization and Masking

Eligible subjects will be randomized in a 1:1:1 ratio in the electronic data capture system. The IP will be dispensed to subjects by trained study personnel only.

The randomization schedule will be computer-generated in the electronic data capture system, and all IP will be masked to the Sponsor, study personnel, and study subjects throughout the study until after the final database has been locked. Appropriate precautions must be taken to prevent unauthorized access to the randomization scheme. Unless the subject's safety requires otherwise, and if time permits, the decision to unmask a treatment assignment is to be made jointly by the Investigator and the Medical Monitor after consultation with the Sponsor.

If unmasking is required during the study, the integrity of the study assessments and collected data will be maintained by limiting access to the unmasked data.

5.4 Dosing Adherence and Dosing Diary

5.4.1 Dosing Adherence

Study personnel will provide training to subjects on proper eye drop administration, proper IP storage when not in use, and proper use of the dosing diary. Subjects will also receive written instructions. Subjects will receive a new supply of IP, as applicable, as indicated in [Appendix 1: Schedule of Procedures and Assessment](#). Study personnel will review subject dosing adherence, as recorded in the dosing diary, at each planned visit and will provide reminders and instruction about the QID dosing schedule and dosing adherence, as needed.

5.4.2 Dosing Diary

Subjects will be asked to record their daily use of IP in a dosing diary that will be collected and reviewed with them during each planned visit. Subjects will receive verbal and written instruction on the proper use of the dosing diary at Visit 3 (Baseline/Randomization), as well as verbal and written instruction on proper eye drop administration and proper IP storage when not in use for dosing.

Empty field entries in the dosing diary will be counted as missed doses, once verified with the subject, for the purpose of measuring dosing adherence. Study personnel will review subject dosing adherence, as recorded in the dosing diary, at each planned visit and will provide reminders and instruction about proper use of the dosing diary, as needed.

5.5 Prior and Concomitant Therapy

For this protocol, a prescription medication is defined as a medication that can be prescribed only by a properly authorized/licensed clinician. Medications to be reported in the electronic case report

CONFIDENTIAL

form (eCRF) are concomitant prescription medications, over-the-counter medications, supplements, and medications provided at Visit 2 (Day of Surgery) as part of site's standard practice during routine cataract surgery. (**Note:** Corticosteroids, oral or topical NSAIDs [excluding low-dose acetylsalicylic acid], and Omidria® [i.e., phenylephrine and ketorolac injection] are prohibited.)

All medications that the subject has taken within 30 days before Visit 1 (Screening) and through Visit 7 (Day 21; End of Study) or exit from the study will be recorded in the eCRF and the subject's source documents. Subjects will be asked for details about any changes in documented medications at all visits. The generic name of the drug, dose, route of administration, duration of treatment (including start and stop dates), frequency, indication, and whether or not the medication was taken due to an AE or as rescue will be recorded for each medication. Prior and concomitant medications will be coded using the World Health Organization Drug Dictionary (WHODrug).

5.5.1 Prohibited Medications and Procedures

Medications that are not explicitly prohibited by the protocol may be used, as needed, throughout the study and recorded as concomitant medications. All medications taken by a subject during the study, whether allowed or prohibited, should be recorded as concomitant medications. [Table 1](#) lists the prohibited medications and procedures for the purposes of the study, as well as the minimum timeframes for discontinuation needed for study eligibility.

CONFIDENTIAL

Table 1 Prohibited Medications and Procedures

Medications and Procedures Not Permitted	Timeframe
Ophthalmic (Study Eye)	
Microinvasive glaucoma surgery, any incisional ocular surgery, or intracameral drug depot to lower IOP	Any history and throughout study
Intraocular surgery	6 months before surgery and throughout study (excluding planned cataract surgery)
Laser surgery, limbal relaxing incision procedure, eyelid surgery Note: Limbal relaxing incisions (laser-assisted and non-laser) are allowed in the study eye at Visit 2 (Day of Surgery)	3 months before surgery and throughout study
Contact lenses	Throughout study and within defined windows before Visit 2 (Day of Surgery) 
 a. Polymethyl methacrylate contact lenses b. Gas permeable rigid lenses c. Extended wear or daily soft lenses 
 a. 6 months before surgery b. 1 month before surgery c. 7 days before surgery
Ophthalmic (Non-study Eye)	
Cataract surgery	14 days before Visit 1 (Screening) or will require cataract surgery <1 day after Visit 2 (Day of Surgery)
General	
Other investigational drug or device	30 days before Visit 1 (Screening) and throughout study
Changes to systemic medication that could have a substantial effect on IOP	30 days before Visit 1 (Screening) and throughout study
Corticosteroids, oral or topical NSAIDs, or Omidria® (i.e., phenylephrine and ketorolac injection) Note: Low-dose acetylsalicylic acid (i.e., baby aspirin or similar) is allowed	1 week before Visit 2 (Day of Surgery) and throughout study

Abbreviations: IOP=intraocular pressure; NSAID=nonsteroidal anti-inflammatory drug

5.5.2 Rescue Medication

Subjects are eligible to be rescued at any time at the Investigator's discretion and placed on appropriate treatment or therapy. Although the use of rescue medication is allowable at any time, advance consultation with the Medical Monitor is preferred, if possible. If a delay in rescue would place the subject at unnecessary risk, the Investigator should proceed with rescue immediately.

The date of rescue medication administration, as well as the name of the rescue medication and dosage regimen, must be recorded as concomitant medications in the eCRF, with a note indicating that the medication was used for rescue. Subjects who require rescue will be counted as treatment failures and undergo follow-up safety assessments and procedures. Every attempt should be made to have subjects continue in the study for safety evaluations, even if subjects discontinue IP. The need for rescue medication itself will not be considered an AE.

CONFIDENTIAL

6 Study Discontinuation/Subject Withdrawal

6.1 Discontinuation of Investigational Product

A subject may be discontinued from IP at any time if the subject, the Investigator, or the Sponsor feels that it is not in the subject's best interest to continue. Subjects may have IP withdrawn by the Investigator due to an AE or due to the need for rescue. Subjects who have IP withdrawn due to an AE should be followed for at least 1 week for safety monitoring, or until the AE has resolved.

6.2 Subject Discontinuation/Withdrawal from the Study

Subjects are free to withdraw from participation in the study at any time upon request. An Investigator may discontinue or withdraw a subject from the study for any reason, including but not limited to the following:

- Adverse event
- Failure to meet randomization criteria
- Lost to follow-up
- Investigator decision
- Pregnancy
- Protocol deviation
- Withdrawal of consent

The reason for subject discontinuation or withdrawal from the study will be recorded in the eCRF. Subjects who sign the informed consent form and are randomized but do not receive IP may be replaced. Subjects who sign the informed consent form, are randomized, receive at least 1 dose of IP, and subsequently withdraw or are withdrawn/discontinued from the study may not be replaced.

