7.1.6 Visit 6 (End of Treatment; Day 14 ± 2)

The following procedures will be performed at Visit 6 (End of Treatment; Day 14 ± 2):

- AE monitoring
- Concomitant medication update
- NPRS
- BCVA
- Slit lamp biomicroscopy
- IOP
- Collect unused IP
- Review dosing adherence and dairy entries
- Urine pregnancy test (only for WOCBP)*
- Schedule or confirm next visit

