7.1.9 Early Termination

In the event that a subject withdraws or is terminated from the study before the end of the study, every attempt will be made to ensure that the subject returns to the site as soon as possible and completes the Visit 7 (End of Study; Early Termination) assessments before being discharged from the study. Any unused IP should be collected during an early termination visit.

CONFIDENTIAL

8 Study Assessments

The Schedule of Procedures and Assessments ([Appendix 1](#): Schedule of Procedures and Assessment) provides a list of study assessments and evaluations to be performed and the timing of each.

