9.4.2.1 Primary Efficacy Analyses

Primary Estimand: The primary estimand is treatment difference between VVN461 (1.0% or 0.5%) and the Vehicle in the proportion of subjects with ACC Grade 0 at Visit 6 (Day 14) in the study eye using the FAS.

Target Population: Subjects undergoing routine cataract surgery who meet the study entry criteria.

Endpoint: Proportion of subjects with ACC Grade 0 in the study eye at Visit 6 (Day 14).

Treatment Condition: Treatment condition is based on randomized treatment.

Population-Level Summary: The difference in proportions in subjects with ACC Grade 0 in the study eye at Visit 6 (Day 14) and the corresponding p-value.

Intercurrent Events and Strategies to Address Intercurrent Events

- Discontinuation of study therapy with continued participation in the study without receipt of rescue therapy
 - Treatment Policy Approach – no imputation; use observed data
- Receipt of rescue therapy (topical corticosteroid) in the study eye
 - Composite Approach – subjects who receive rescue therapy at or before the assessment visit will be assumed to have failed the primary endpoint
- Missing data with or without withdrawal, regardless of reason
 - Hypothetical Approach – no imputation; analysis will be based on subjects who have an evaluable anterior chamber in the study eye at Visit 6 (Day 14)

Pearson's chi-square will be used to test the primary endpoint between the 2 different doses of VVN461 vs the Vehicle. The primary analysis will also be performed on the PP Analysis Set.

CONFIDENTIAL

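### Section 6.2 lets an investigator withdraw a randomized, dosed subject from the study for a protocol deviation; if this happens before Day 12, an avoidable gap opens in the primary outcome

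*Protocol*

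**What the plan says.** **Withdrawal.** Protocol 6.2: "An Investigator may discontinue or withdraw a subject from the study for any reason, including but not limited to the following". The list that follows includes AE, investigator decision and protocol deviation. This is withdrawal from the study; stopping investigational product (IP) is covered separately in 6.1. The last sentence of 6.2 concerns subjects who "are randomized, receive at least 1 dose of IP, and subsequently withdraw or are withdrawn/discontinued from the study may not be replaced", so the permission is not confined to exits before randomization.

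**Exit examination.** Under Protocol 7.1.9, for a subject who leaves early, "every attempt will be made to ensure that the subject returns to the site as soon as possible" and completes the Visit 7 assessments. These include slit lamp biomicroscopy (7.1.7). SAP 9.7.1.5 leaves early-termination data out of the summaries unless the exit falls within the window of a visit. Visit 6 is Day 14 ± 2 (Protocol 7.1.6 and Appendix 1).

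**Primary analysis.** The FAS is everyone randomized (Protocol 9.3). Protocol 9.4.2.1 applies treatment policy to "Discontinuation of study therapy with continued participation in the study without receipt of rescue therapy" and uses the observed grade. Rescue counts as failure. For missing data there is no imputation: "analysis will be based on subjects who have an evaluable anterior chamber in the study eye at Visit 6 (Day 14". SAP 9.7.1.5.1 adds that exits for lack of efficacy or AE count as failures, and it plans a control-based multiple imputation sensitivity analysis.

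**Deviations.** Subjects with significant deviations are removed from the PP set, by a decision taken before lock and unmasking (Protocol 9.3, SAP 9.7.1.1.1).

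**The concern.** The analysis plan and the withdrawal rule pull in different directions. The FAS keeps every randomized subject, and the PP set is where deviations are meant to count. Yet 6.2 lets an investigator end a subject's study participation because of a deviation, and that removes the subject from the FAS primary comparison as well as from the PP set. The decision is discretionary, is taken after randomization and could be related to how the eye is doing.

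A Visit 6 grade that was never taken cannot be recovered in the analysis. It can only be modeled, as the planned sensitivity analysis does. The loss is avoidable because the Visit 6 examination is already on the schedule for every subject.

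**Working it through.** **1. Which exits are exposed**

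- Visit 6 window: 14 - 2 = Day 12 to 14 + 2 = Day 16. An exit examination before Day 12 cannot count as Visit 6.
- How the plan treats an exit before Day 12, by reason:

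| Exit before Day 12 | Treatment in the primary analysis | Grade lost to the analysis? |
|---|---|---|
| Rescue given | Failure (composite) | No |
| AE or lack of efficacy | Failure (SAP composite) | No, scored by rule |
| IP stopped, subject stays in the study, no rescue | Observed Visit 6 grade | No |
| Investigator withdraws for deviation or by own decision, no rescue | No Visit 6 grade, no imputation | Yes, left out |

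Only the last row is at issue. The follow-up minimum in 6.1 ("should be followed for at least 1 week for safety monitoring, or until the AE has resolved") applies to IP stopped for an AE, so it does not cover that row.

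**2. The plan's own figures**

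Inputs from Protocol 9.2: Vehicle 30%, difference 35 points (active 65%), 30 evaluable per arm, two-sided 0.05, Pearson chi-square, 10% drop-out.

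- Mean rate = (0.30 + 0.65)/2 = 0.475.
- z = [0.35 × √30 - 1.96 × √(2 × 0.475 × 0.525)] / √(0.30 × 0.70 + 0.65 × 0.35) = (1.917 - 1.384)/0.661 = 0.806, so power = 79.0%. Exact enumeration gives 79.8%. The stated 80% reproduces.
- 30/0.9 = 33.3, rounded up to 34 per arm; 3 × 34 = 102, as stated.

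**3. Effect of one excluded subject**

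At 34 per arm the planned rates give 0.65 × 34 = 22.1, taken as 22, and 0.30 × 34 = 10.2, taken as 10. P-values are Pearson chi-square without continuity correction.

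| Case | Active | Vehicle | Difference (points) | Change | p |
|---|---|---|---|---|---|
| Nobody excluded | 22/34 | 10/34 | 35.3 | n/a | 0.0036 |
| Active non-responder out | 22/33 | 10/34 | 37.3 | +2.0 | 0.0023 |
| Active responder out | 21/33 | 10/34 | 34.2 | -1.1 | 0.0050 |
| Vehicle non-responder out | 22/34 | 10/33 | 34.4 | -0.9 | 0.0048 |
| Vehicle responder out | 22/34 | 9/33 | 37.4 | +2.1 | 0.0021 |

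**4. One excluded subject in each arm**

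- Same kind in both arms: 22/33 vs 10/33 or 21/33 vs 9/33, both 36.4 points (+1.1), p about 0.003.
- Opposite kinds: 21/33 vs 10/33 = 33.3 (-2.0), p = 0.0067; 22/33 vs 9/33 = 39.4 (+4.1), p = 0.0013.

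**5. More exits (assumption, for scale only)**

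Suppose 2 of 34 active subjects are left out, with true rates of 65% and 30%. The difference then lies between (22.1 - 2)/32 - 0.30 = 32.8 points, if both would have responded, and 22.1/32 - 0.30 = 39.1 points, if neither would have.

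**The case against.** **The wording is permissive.** Section 6.2 says an investigator may withdraw a subject; nothing requires or encourages it for a deviation. The list also serves exits before randomization. No document suggests how often such exits will happen, and the number could be zero. This stands, and it is why the total effect cannot be stated.

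**Retention is already implied.** The protocol separates stopping IP (6.1) from leaving the study (6.2). Section 6.3 has sites counsel subjects who miss a visit to keep to the schedule. Section 5.5.2 asks for every attempt to keep subjects in the study for safety evaluations even if they stop IP, and slit lamp is one of those evaluations (8.2). A reader might infer from the absence of an explicit retention sentence that everyone who stops IP is lost. The documents do not support that: a subject who stops IP and is not withdrawn stays on the Visit 6 schedule by default. The objection does not reach subjects whom the investigator actively withdraws.

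**AE exits.** A reader might also count these as lost outcomes. They are not. The SAP deliberately scores them as failures, so they stay in the analysis, and any effect they have comes from that chosen strategy.

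**Mitigation exists.** Under Protocol 5.3, "all IP will be masked to the Sponsor, study personnel, and study subjects throughout the study until after the final database has been locked". The 10% allowance covers about 4 losses per arm, and control-based imputation is planned for the primary endpoint. All of this limits the consequence; none of it recovers the missing grade.

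**Retention has its own problem.** Some deviations are use of a prohibited anti-inflammatory, such as an NSAID (Protocol 5.5.1), while the estimand's rescue rule names topical corticosteroid only. A retained subject who took an NSAID outside rescue could contribute a Grade 0 with no stated intercurrent-event rule. This stands, and the fix has to deal with it.

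**Conclusion.** The point holds for one narrow class: investigator withdrawals for a deviation or by discretion, before Day 12, without rescue, AE or lack of efficacy. Those subjects drop out of the primary FAS analysis although the schedule would have supplied their grade.

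At the planned rates each one moves the difference by about -1.1 to +2.1 points, in either direction, with p between 0.002 and 0.005. This assumes 34 per arm, response at the planned 65% and 30%, and no other missing data. The frequency is unknown, so no total is given.

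A reader might go further and infer a bias toward the drug or a result at risk. The documents do not support either. The decisions are masked, the shift can go both ways, and like exits in both arms largely cancel. Near p = 0.05 a single lost subject could tip the test, but that is true of any lost subject, can go in either direction, and says nothing particular about 6.2. This is a cheap improvement to the plan.

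**What to change.** **Protocol 6.2, add:** *After randomization, a protocol deviation is not by itself a reason to withdraw a subject from the study. Such subjects, and subjects who stop IP without rescue, attend all remaining scheduled visits, including Visit 6 SUN grading, unless they withdraw consent or further visits are unsafe.*

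**SAP 9.7.1.5.1, add:** non-rescue use of a prohibited anti-inflammatory (corticosteroid or NSAID) before Visit 6 is handled like rescue, as failure on the primary endpoint. Without this rule, subjects retained after such a deviation would have no defined handling.

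Investigator discretion on safety grounds and exits before randomization stay as they are.

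**Cost:** a short amendment, one added SAP rule and a few attended visits by subjects off IP. No new procedure is needed, because the visits and the grading are already scheduled.
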